#### **10.b.vi Follow-Up Visit (T2)**

T2 will occur approximately 3 months after T1. Participants will self-obtain specimens (throat, urogenital, and rectal) to monitor incident gonorrhea (GC) and chlamydia (CT). Participants will also provide urine and blood specimen to monitor PrEP adherence, creatinine levels, syphilis, pregnancy, and HIV (provided by PPP per their standard of care). PrEP adherence, creatinine levels, and pregnancy testing will only be performed for women taking PrEP. Participants will complete a semi-structured interview to explore psycho-social factors associated with HIV/STI risk, and engagement across key transition points in the PrEP care continuum including (1) attending initial clinical appointment; (2) enrolling in health insurance or medication assistance programs for uninsured participants; (3) accepting a PrEP prescription; (4) filling the PrEP prescription; (5) adhering to PrEP using a validated three-item self-report measure for anti-retroviral therapy adherence in the last 30 days, modified for PrEP adherence, (6) and returning for follow-up care. These activities represent critical moments when women could disengage or need additional support to remain in care. If participants disengage in care at any point in the PrEP continuum, we will ask about the factors motivating this decision. Then, we will assess the acceptability of receiving PrEP care at the SEP, intention to remain engaged in PrEP care, and the factors motivating them to do so (or drop out of care). A draft of the semi-structured interview is in Appendix 3. Participants will receive \$25 for this visit. Any participant needing clinical follow-up after T2 will be scheduled with the CP outside of study hours. Women who test positive for pregnancy will not be eligible for follow-up PrEP care at PPP. They will be referred to their primary care provider (PCP). If women do not have a PCP we will work with them to establish care.

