#### **10.b.viii Follow-Up Visit (T3)**

T3 will occur approximately 3 months after T2. Participants will self-obtain specimens (throat, urogenital, and rectal) to monitor incident gonorrhea (GC) and chlamydia (CT). Participants will also provide blood specimen to

monitor creatinine levels (if someone is taking PrEP only), syphilis and HIV (provided by PPP per their standard of care). Urine specimen will be collected to monitor pregnancy for women taking PrEP. They will also sign a release of information (Appendix 14) to allow us to contact the pharmacy where they report filling their PrEP prescription to verify fill dates. Participants will complete a semi-structured interview to explore psycho-social factors associated with HIV/STI risk and engagement across key transition points in the PrEP care continuum. If participants disengage in care at any point in the PrEP continuum, we will ask about the factors motivating this decision. Then, we will assess the acceptability of receiving PrEP care at the SEP, intention to remain engaged in PrEP care, and the factors motivating them to do so (or drop out of care). A draft of the semi-structured interview is in Appendix 15. Participants will receive \$35 for this visit. Any participant needing clinical follow-up after T3 will be scheduled with the CP outside of study hours. Women who test positive for pregnancy will not be eligible for follow-up PrEP care at PPP. They will be referred to their primary care provider (PCP). If women do not have a PCP we will work with them to establish care.

We will also recruit a purposive sample of WWID who initiate but disengage (n=15) and WWID who adhere/remain engaged in PrEP for 6 months (n=15) to participate in an in-depth qualitative interview. Recruitment will be done so that we elicit diversity in opinions, challenges, and successful strategies to engagement. Interviews will elicit previously unmeasured but critical factors impacting women's decisions and will also explore individual and structural facilitators and barriers that hinder or support engagement at each stage of the care continuum drawing from the BMVP. A preliminary draft of the in-depth interview is in Appendix 5. This subset of participants will receive \$20 for participating in the qualitative interview.

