#### **10.e Retention**

To decrease attrition, we will develop a tracking protocol to ensure multiple points of contact with participants. Using their preferred mode of contact, we will remind participants of study visits and follow up with those who "no show." For each "no show," we will follow up twice weekly for 3 weeks. Any participant failing to contact staff within 3 weeks will be considered lost to follow up. However, they will not be withdrawn from the study. Using these procedures, we anticipate >85% retention.

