**Medication adverse effects:** There is minimal risk of harms associated with the use of daily FTC/TDF as PrEP by HIV-uninfected individuals. Medication intolerance during clinical trials included nausea, vomiting, abdominal pain, and diarrhea. These effects occurred in a minority of PWID (<20%) participating in the Bangkok Tenofovir Trial and most participants reported symptoms had resolved by the 2nd month. Of these side effects, only nausea and vomiting were statistically higher among PWID on Tenofovir than those taking the placebo. Tenofovir has been linked to renal impairment when used for HIV treatment, and a meta-analysis of 3 PrEP efficacy studies found that use of TDF/FTC was associated with small but statistically significant decreases in renal function. However, increased creatinine was observed in only 3% of patients in the Bangkok Tenofovir study, and other studies have found that changes in renal function with use of PrEP are reversible upon discontinuation of TDF/FTC. To monitor for potential medication-related renal toxicity, we will measure creatinine levels at T1 and T2 (which will be scheduled over 3 months) as is recommended in the current CDC PrEP clinical guidelines and is considered standard of care. We will also follow-up with participants accepting a PrEP prescription approximately 2 weeks after T1. During that check-in we will assess for medication intolerances, assess adherence, and provide adherence counseling. Any participant with intolerances (i.e. that do not resolve by 2 months after use of PrEP) or any abnormal renal function testing will be scheduled with the CP. Those with any persistent intolerances or abnormal renal function will be referred to their primary care provider (PCP). If women do not have a PCP we will work with them to establish care.

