## 12. DATA MANAGEMENT

### 12a. Data analysis plan

**Aim 1. Describe WWID's engagement in the PrEP care continuum among WWID.** We will use summary statistics (frequency and percent with associated error terms) to describe participant engagement across key transition points in the care continuum including: (1) returning for STI results at T1; (2) enrolling in health insurance or medication assistance programs for uninsured participants between T0 and T2; (3) accepting a PrEP prescription; (4) filling the PrEP prescription or providing authorization for the PrEP prescription to be filled between T0 and T2; (5) adhering to PrEP between T1 and T3; (6) and returning for follow-up care at T2 and T3. Descriptive analyses will also be used to characterize adherence in terms of perfect defined as a dose of TFV within 48 hours (>1000 ng/mL), low adherence (>10 to >100 ng/mL), and non-adherence as defined by last dose more than one week prior (<10 ng/mL). We will also compare concordance of self-reported adherence to urinalysis.

**Aim 2. To assess the impact of predisposing, enabling, and need-related factors on WWID's engagement in the PrEP care continuum.** We will test the association between BMVP factors and WWID's engagement at each stage outlined above using procedures that have been used previously to describe gaps in the PrEP care continuum for MSM. Independent variables will represent each of the model's domains including: predisposing factors, enabling factors, and need (drawn from Table 1). In the case WWID do not populate each stage describe above we will collapse engagement into an ordered categorical variable similar to how we are approaching qualitative data. In this case, engagement would be treated as a 3-level variable: never initiated PrEP vs those who initiate but disengage vs those who remain engaged for 3 months. Inferential statistics will be used to identify associations between factors in the model and PrEP engagement. For

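### A urine result that shows only a recent dose is labelled 'perfect' adherence to a daily regimen, so the reported percentage can only overstate the share taking every dose

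*Combined protocol and SAP*

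**What the plan says.** Section 12a (Aim 1) lists adherence as step 5 of the care continuum, for the period "adhering to PrEP between T1 and T3", and names no measure for it there. It then adds a description by urine TFV. The top class will "characterize adherence in terms of perfect defined as a dose of TFV within 48 hours (>1000 ng/mL". The other classes are "low adherence (>10 to >100 ng/mL), and non-adherence as defined by last dose more than one week prior (<10 ng/mL". Self-report is to be compared with the urine result for concordance.

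The regimen is daily: section 10.e on lessening risk refers to the "use of daily FTC/TDF as PrEP by HIV-uninfected individuals", and sections 13 and 15 say the same.

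On sampling, section 10.b.vi (T2) says "Participants will also provide urine and blood specimen to monitor PrEP adherence" and limits this testing: "PrEP adherence, creatinine levels, and pregnancy testing will only be performed for women taking PrEP". Section 10.b.viii (T3) gives a different purpose for urine: "Urine specimen will be collected to monitor pregnancy for women taking PrEP". The section 10 overview mentions medical-monitoring tests at T3 for initiators but does not say which.

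Two other sources bear on adherence. Section 10.b.vi ties continuum step 5 to a three-item self-report covering the last 30 days. Section 10.b.viii obtains a release so that the pharmacy can verify fill dates.

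**The concern.** In a daily regimen, 'perfect' means that no dose was missed. The class so labelled requires only one dose in the last two days, on one sample. The bottom class is also defined by time since the last dose, so the scale measures recency at both ends. At the top, a recency result is given an adherence name.

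The error has one direction. On the plan's own cut-off, a woman who doses daily stays in the top class, and a woman who doses intermittently may be moved up into it. Section 8 says the findings will feed an application for an intervention on non-initiation or suboptimal adherence. Intermittent users are part of that target, and this label makes them harder to see.

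**Working it through.** **Plan's own figure.** The documents state no expected percentage 'perfect' and no calculation behind the class, so there is nothing to reproduce. The check applies the plan's rule to assumed dosing patterns.

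**Inputs from the documents**
- Rule for 'perfect': last dose within 48 hours, equated with urine TFV above 1000 ng/mL (12a).
- Regimen: daily (10.e on lessening risk, 13, 15), so a 48-hour window holds two dosing days.
- Drug-level samples listed in the detailed procedures: one, at T2 (10.b.vi); T3 urine is for pregnancy (10.b.viii).
- Period for step 5: T1 to T3, about 6 months (12a and section 10).

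**Assumptions that are not in the documents**
- A level above 1000 ng/mL means exactly that a dose was taken in the last two days.
- Each day's dose is taken independently with probability p = (doses per week)/7.

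**Formula.** A woman misses the top class only if she skipped both days, so P('perfect') = 1 − (1 − p)².

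| Doses per week | Share of daily doses taken | P('perfect') on one sample |
|---|---|---|
| 1 | 1/7 = 14% | 1 − (6/7)² = 13/49 = 26.5% |
| 2 | 2/7 = 29% | 1 − (5/7)² = 24/49 = 49.0% |
| 3 | 3/7 = 43% | 1 − (4/7)² = 33/49 = 67.3% |
| 4 | 4/7 = 57% | 1 − (3/7)² = 40/49 = 81.6% |
| 5 | 5/7 = 71% | 1 − (2/7)² = 45/49 = 91.8% |
| 6 | 6/7 = 86% | 1 − (1/7)² = 48/49 = 98.0% |
| 7 | 100% | 100% |

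Only the last row is perfect adherence in the ordinary sense. Every other row puts some women in the same class, and no row takes a daily user out of it. That gives the direction.

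**Would a second sample cure it?** Suppose the unspecified T3 tests included a drug level, and 'perfect' required both results above the cut-off. With a constant dosing rate and independent samples, the chances at 2, 3 and 4 doses a week are (24/49)² = 24%, (33/49)² = 45% and (40/49)² = 67%. The error shrinks but remains.

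**Coverage.** Taking 6 months as about 180 days, one 48-hour window covers 2/180 = 1.1% of the step 5 period.

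**The case against.** The strongest reply is that the plan does less with this class than the label suggests.

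- *The cut-off is disclosed.* The definition stands beside the label, so a careful reader can decode it. That is true, but a percentage reported as 'perfect' will be read as adherence, and disclosure does not make the word accurate.
- *Step 5 has its own measure.* Section 10.b.vi ties it to a 30-day self-report, and 12a introduces the urine classes as a further description. This stands. A reader might infer that the urine class is the step 5 outcome for T1 to T3; the documents do not say so. Nor do they make it a headline result: section 9 names acceptability and feasibility, and 12b calls the study exploratory.
- *There are cross-checks.* Concordance with self-report could expose some partial users, and fill dates could show gaps in supply. Neither is a condition for the label. A woman who truthfully reports missed doses would simply appear discordant with a 'perfect' urine result, and 12a does not say how such a conflict is resolved.
- *The size is not known.* This stands. The documents give no adherence distribution, and the number tested at T2 is not stated. The 61 initiators expected in 12b need not all be tested, because section 10.b.vi tests only women taking PrEP at that visit.

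A reader might also infer that alternate-day users are always classed 'perfect', or that one tablet before a visit guarantees it, since section 10.e (Retention) says "we will remind participants of study visits". The documents do not support either as a fact. Classification is by concentration, and nothing in them shows that an isolated dose, or one nearly 48 hours old, exceeds 1000 ng/mL. The reminders are a retention measure, and the protocol does not say that they mention drug testing.

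**Conclusion.** The point holds as a fault of labelling and interpretation. The top urine class measures how recent the last dose was. If the plan's cut-off is accepted, the percentage called 'perfect' can only overstate the share of women taking every daily dose. Neither the concordance comparison nor the fill dates change that label.

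The direction follows from the plan's own definition. The size does not: 49%, 67% and 82% at 2, 3 and 4 doses a week are illustrations that assume independent daily dosing and an exact match between the cut-off and a dose in the last 48 hours. They are not forecasts for this cohort, and they do not show that the step 5 result itself is wrong, because section 10.b.vi gives that step a separate measure. The change should be made before the adherence results are reported.

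**What to change.** In section 12a:

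1. Rename the class above 1000 ng/mL 'recent dosing (last dose within 48 hours)' and drop 'perfect'.
2. State that the class does not estimate the proportion of daily doses taken.
3. Name the 30-day three-item self-report, already assigned in section 10.b.vi, as the measure for step 5, with urine TFV as confirmation of recent use. Give the period that each source covers, and say whether the self-report is repeated at T3, since the T3 section does not name it.
4. Use pharmacy fill dates as supporting evidence of supply only. Report days covered only if days supplied is also obtained; section 10.b.viii obtains fill dates alone, and a filled prescription does not show that tablets were taken.

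Items 1 to 3 change wording only, using data already planned. Days covered would need one more item from the pharmacy. No visit, test or treatment changes. The price is a more modest claim: recent use in urine plus self-reported adherence over 30 days, in place of a percentage with perfect adherence.

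### The planned concordance sets a 30-day self-report against urine bands based on the last dose, so disagreement cannot be read as misreporting

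*Combined protocol and SAP*

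**What the plan says.** Section 10.b.vi (T2) describes the self-report as "adhering to PrEP using a validated three-item self-report measure for anti-retroviral therapy adherence in the last 30 days, modified for PrEP adherence". Urine for PrEP adherence is collected at the same visit.

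Section 12a (Aim 1) sorts the urine results into three bands. The top one is "perfect defined as a dose of TFV within 48 hours", tied to a concentration above 1000 ng/mL. The bottom one is a last dose more than one week earlier, below 10 ng/mL. The middle one, low adherence, has no time window, and its printed limits (above 10 to above 100 ng/mL) leave 100–1000 ng/mL without a clear place. The plan then adds: "We will also compare concordance of self-reported adherence to urinalysis". It names no agreement statistic, no mapping of the 30-day scale onto the bands and no self-report cut-off, and it does not say how discordance will be interpreted.

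On who is tested at T2, section 10.b.vi says: "PrEP adherence, creatinine levels, and pregnancy testing will only be performed for women taking PrEP". Section 10 instead says that the women who initiated PrEP receive the monitoring tests at T2.

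**The concern.** Agreement between two measures says something about reporting accuracy only if both measure the same thing. Here one covers 30 days of pill-taking and the other depends on how recent the last dose was. A woman who took half her pills and says so can still have a urine result in the top band because she took one yesterday. A woman who took every pill until ten days ago and says so will have a urine result in the bottom band. Both reports are accurate, and both count as discordant.

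Two results are at stake. The first is the concordance figure: if it is low, the investigators cannot separate misreporting from the difference in windows. The second is the adherence distribution itself, which is stage 5 of the continuum that Aim 1 describes. A single sample showing a dose in the last two days is labelled perfect, and this could hide women who need adherence support. Section 12a says that its analyses are meant to inform intervention design and later studies.

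**Working it through.** The plan states no agreement level, kappa or sample size for this comparison, so there is no figure to reproduce. The check asks what agreement would be if every woman reported exactly what she took.

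**Inputs from the documents.** Self-report window: 30 days (10.b.vi). Top urine band: a dose in the last 2 days. Bottom band: no dose in the last 7 days (both 12a).

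**Assumptions, not in the documents.** The middle band is what remains, a last dose 2–7 days ago. Days are independent with dosing probability p. A report counts as high at 80% (24 of 30 days) or 90% (27 of 30). For three categories, zero days is none and anything between is intermediate.

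**Fixed p.** P(top band) = 1 − (1 − p)².
- p = 0.3: 1 − 0.7² = 0.51.
- p = 0.5: 1 − 0.5² = 0.75, while the chance of at least 27 of 30 days is below 0.001.
- p = 0.75: 1 − 0.25² = 0.94, against 0.04 for at least 27 of 30 days.
- p = 0.9: 1 − 0.1² = 0.99, against 0.65 for at least 27 of 30 days.

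**p uniform over 0–100%, exact two-by-two.** Days taken, s, are then equally likely from 0 to 30.
- P(high) = 7/31 = 0.2258 at the 80% cut and 4/31 = 0.1290 at the 90% cut.
- P(not top band) = 1/3, the mean of (1 − p)².
- Given s, P(no dose in the last 2 days) = (30 − s)(29 − s)/870. So P(high and not top band) = (30 + 20 + 12 + 6 + 2)/870/31 = 0.0026 at the 80% cut, and (6 + 2)/870/31 = 0.0003 at the 90% cut.
- Agreement = P(high) + P(not top band) − 2 × P(high and not top band). At 80%: 0.2258 + 0.3333 − 0.0052 = 0.554. At 90%: 0.1290 + 0.3333 − 0.0006 = 0.462.
- Kappa at 80%: chance agreement is 0.2258 × 0.6667 + 0.7742 × 0.3333 = 0.409, so kappa = (0.554 − 0.409)/(1 − 0.409) = 0.25.
- Direction at 80%: not high but top band = 0.6667 − (0.2258 − 0.0026) = 0.443; high but not top band = 0.003. Of the women in the top band, 0.443/0.6667, about two thirds, took fewer than 80% of doses.

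**Full range by simulation** (400,000 women; p uniform over 0–100% or 20–100%; both cuts):
- Two-by-two agreement is 37–55%, kappa 0.10–0.25. The low end is the 20–100% spread with the 90% cut.
- Three-category agreement is 35–46%, kappa 0.09–0.22.
- Across the four two-by-two scenarios, 44–63% of women have urine better than their report, and under 0.4% have the reverse.

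**Other patterns, three categories.**
- U-shaped use, Beta(0.3, 0.3), with cuts at 24, 27 or 30 days: 49–67%, kappa 0.33–0.51.
- Mostly high use, Beta(8, 2), same cuts: 10–65%, kappa 0.01–0.12.
- All doses or none: 100%, kappa 1.
- Daily users who stopped t days ago, t equally likely from 0 to 29, cut 27: they agree for t = 0, 1, 4, 5 and 6, so 5/30 = 17% (kappa 0.02). In the other 25 cases the report looks better than the urine.

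**The case against.** The strongest reply is that the size is assumed. The documents give no dosing pattern and no cut-off, and the illustration moves from very poor to perfect agreement as these change. A coarse comparison, any use in 30 days against detectable urine, gives 90% or more raw agreement under the independent-day patterns. The comparison is one descriptive sentence in a study that section 12b calls exploratory, and the plan defines its top label by dose window and concentration in the same sentence. The T2 interview (Appendix 3) is not available here and may already contain a last-dose item. All of this stands, and it limits the weight of the point. It does not remove the mismatch, because both windows are in the text and nothing there aligns them.

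Three stronger readings are tempting, and the documents do not support them.

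- A reader might infer that honest answers must look discordant, or that any disagreement comes from the window alone. Women who took every dose or none would agree, and real misreporting can coexist with the window effect.
- A reader might infer that low agreement would make participants look like over-reporters. Under intermittent dosing the error runs almost wholly the other way, towards apparent under-reporting. Only recent stoppers look like over-reporters. The plan does not say how it would read discordance.
- A reader might infer from the T2 restriction to women taking PrEP that part of the agreement table must stay empty. Section 10 has women who initiated PrEP being tested, and section 12a plans a band for a last dose over a week old, which expects some lapsed women among those tested. The term is undefined; an empty cell is not shown.

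**Conclusion.** The concern holds as a mismatch of windows. Followed as written, the plan yields a concordance figure that mixes misreporting with the difference between 30 days and the last dose, and a top label that overstates adherence for intermittent users. The direction of the artefact depends on the pattern of use, so the overall figure cannot be corrected afterwards without knowing that pattern.

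The agreement percentages are illustrations under honest reporting and assumed dosing and cut-offs, not forecasts for this cohort. No error rate is affected, because the analysis is descriptive; the effect is on interpretation. The change is worth making before T2 data are analysed, and it is not a fundamental flaw in the study.

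**What to change.** - At T2, ask one question on the time of the last dose, with answers in the urine bands: within 48 hours, 2–7 days, more than 7 days. If Appendix 3 already has such an item, name it in section 12a and use it.
- Base concordance on that item, with weighted kappa for the ordered bands. An honest answer then agrees by construction, apart from assay and metabolic variation, so remaining discordance can be interpreted.
- Report the 30-day scale against urine only as a correlation.
- Label the top band as a dose within 48 hours, not as perfect adherence. Reconcile the printed concentration limits so that every result falls in one band.
- Reconcile women taking PrEP (10.b.vi) with women who initiated PrEP (section 10), so that it is clear who contributes a urine result to the table.

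The cost is one extra interview question and revised analysis wording. If the clarified group includes women who report having stopped, a few more assays may be needed.

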#### **10.f Laboratory Tests**

Philadelphia Department of Health will perform STI testing using the AC2 CT/GC assay on the Hologic Tigris platform, Hepatitis B testing will be performed on the Abbott Architect and creatinine testing will be performed on the Beckman Coulter DXC. Positive test results will be reported to disease control agencies per local regulations. This process is outlined in the informed consent. Philadelphia FIGHT will perform drug-level monitoring using a semi-quantitative liquid chromatography-tandem mass spectrometry urine assay with high sensitivity and specificity to monitor TFV. Specimens will be processed and confidential results returned within 7 days. Pregnancy tests will be performed by the CP using a rapid urine assay to detect human chorionic gonadotropin hormone.

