continuous variables, such as age or number of sex partners, we will provide medians with associated interquartile ranges and utilize independent samples t-tests or Mann-Whitney U tests to identify differences in medians between women who do or do not engage at each stage. For categorical and binary variables, such as race/ethnicity or insured (yes/no),  $\chi^2$  tests will be used to detect differences in factors that may be associated with PrEP engagement. Assessing the factors impacting engagement is critical for the design of intervention strategies, as different populations of WWID may need different cues to action or support in order to engage at each stage. These analyses will inform future study designs and sample size.

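### Aim 2 compares adherence only as engaged or not, with no cut stated, although graded adherence data are already collected; an ordered test is a cheap gain of about 0 to 13 points of power over the better cut

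*Combined protocol and SAP*

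**What the plan says.** Section 12a, Aim 1, lists six continuum stages; the fifth is "adhering to PrEP between T1 and T3". Aim 2 then states: "We will test the association between BMVP factors and WWID's engagement at each stage outlined above". For continuous factors the plan will "utilize independent samples t-tests or Mann-Whitney U tests" to "identify differences in medians between women who do or do not engage at each stage". Categorical and binary factors go to chi-square tests. Nowhere does the plan say what counts as adherent in this comparison.

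Adherence is measured in graded form in two ways.

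- Self-report: the T2 interview (10.b.vi) covers "adhering to PrEP using a validated three-item self-report measure for anti-retroviral therapy adherence in the last 30 days", modified for PrEP.
- Urine: 10.f Laboratory Tests describes a "semi-quantitative liquid chromatography-tandem mass spectrometry urine assay with high sensitivity and specificity to monitor TFV". Section 12a sorts the result into perfect (above 1000 ng/mL), low, and non-adherence (below 10 ng/mL). Their role is stated under Aim 1: "Descriptive analyses will also be used to characterize adherence in terms of perfect defined as a dose of TFV within 48 hours". They are also compared with self-report for concordance.

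Aim 2 has one ordered variable, a fallback used only if some stages are not populated. Its levels are never initiated, initiated then disengaged, and engaged for 3 months. That grades overall engagement, not adherence among women on PrEP.

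Section 12b (Power analysis) calls the study exploratory and states no significance level, effect size or power.

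**The concern.** Stage 5 has one of the smallest groups in Aim 2 and the most finely graded outcome. If it is tested as yes or no, women with low adherence must be pooled either with the perfect group or with the non-adherent group, and each pooling discards one of the two contrasts. Because no cut is stated, that choice could be made after the data are seen, and the list of associated factors may depend on it. Section 12a calls these analyses critical for designing intervention strategies and says they will inform later study designs and sample sizes. A real predictor of adherence that is missed here would not be carried forward.

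**Working it through.** **1. The plan's own figure.** Section 12b gives 200 women, 86% willing, 50% of those initiating, 15% attrition per visit, and a final sample of 122 split 61/61. 200 × 0.85³ = 122.8, and half of that is 61.4, so both figures reproduce. The even split does not use the 86%: 0.86 × 0.50 = 43%, and 122.8 × 0.43 = 52.8 initiators.

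**2. Size of the stage 5 group at T2.** 200 × 0.86 × 0.50 = 86 initiators. After two visits with 15% loss, 86 × 0.85² = 62.1. With the even split instead, 200 × 0.85² × 0.50 = 72.3. For urine these are ceilings, because 10.b.vi restricts the adherence assay to women taking PrEP. I use 62.

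**3. Power with a binary factor.** The plan gives no effect size or band distribution, so these are assumptions: n = 62, two equal groups, a latent normal adherence scale shifted by 0.7 SD, and two-sided 5%. The ordered test is Mann-Whitney on three bands; the yes/no test is chi-square without continuity correction. The first four rows use 4000 runs each and the last four 3000. Simulation error is up to about 0.9 points per figure (√(0.6 × 0.4 / 3000) = 0.009).

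| Non / low / perfect (%) | Three bands | Perfect vs rest | Any vs none | Gain over better cut |
|---|---|---|---|---|
| 33/33/33 | 0.677 | 0.549 | 0.548 | 0.128 |
| 50/30/20 | 0.652 | 0.465 | 0.602 | 0.050 |
| 20/40/40 | 0.672 | 0.574 | 0.456 | 0.098 |
| 60/30/10 | 0.606 | 0.327 | 0.568 | 0.038 |
| 5/45/50 | 0.625 | 0.614 | – | 0.011 |
| 5/25/70 | 0.552 | 0.535 | – | 0.017 |
| 5/15/80 | 0.466 | 0.464 | – | 0.002 |
| 45/5/50 | 0.598 | 0.600 | – | −0.002 |

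Across shifts of 0.6 to 0.8 SD, the first four splits give gains of about 2 to 13 points over the better cut and 12 to 32 points over the other. With n = 40, a 0.7 SD shift and even bands, power is 0.474 against 0.400 and 0.393. With no true effect, all tests rejected in about 5 to 6% of runs.

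**4. Power with a continuous factor.** This is the case to which the two-group wording directly applies. The factor is assumed to correlate 0.3 or 0.4 with latent adherence, with n = 61 or 53 and 3000 runs. Spearman on three bands is compared with Mann-Whitney on each cut.

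- n = 61, correlation 0.4, equal thirds: 0.799 against 0.662 (perfect vs rest) and 0.666 (any vs none).
- n = 53, correlation 0.3, split 70/20/10: 0.401 against 0.222 and 0.373.

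Over all 16 combinations of size, correlation and split (none with a band below 10%), the ordered test gained 2.8 to 13.5 points over the better cut and 10.3 to 26.7 over the other.

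**The case against.** The case for leaving the plan alone has several parts.

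- **The text does not explicitly cut the adherence bands.** The engage-or-not wording covers six stages, most of them naturally yes/no, and sits in the sentence on continuous factors. The chi-square sentence would allow a factor-by-three-band table. This stands in part: for categorical factors the two-level reading is an inference. But a chi-square test ignores the order of the bands, and for continuous factors the two-group comparison is explicit.
- **The urine bands are not usable as printed.** Low runs from above 10 to above 100 ng/mL, and 100 to 1000 ng/mL is assigned to no band. This stands and must be repaired first. A yes/no cut on the same bands has the same gap.
- **Urine measures something else.** The bands describe time since last dose, and 10.b.vi collects urine for adherence at T2; the T3 urine in 10.b.viii is for pregnancy. Stage 5 spans T1 to T3. This stands, so the urine result needs a label and should not be the only ordered outcome.
- **The lowest band may be sparse**, since women who have stopped are not assayed. This stands; the gain is then 0 to 2 points.
- **The study is exploratory and follows procedures already used for the PrEP continuum in MSM.** This stands as to severity. It gives no reason to discard the grading for this one stage.

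A reader might also infer a larger gain from analysing the urine level as a continuous measurement. The documents do not support that: the assay is semi-quantitative and the plan describes its results only in bands.

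**Conclusion.** The point holds as a modest, cheap improvement. As written, Aim 2 compares stage 5 in two groups with no stated cut, while graded data that the study already collects serve only description and concordance. An ordered test on three bands gains about 0 to 13 points of power over the better yes/no cut and more over the other, and it was not materially worse in any scenario tried. The direction is secure. The size is not: it rests on an assumed 0.7 SD shift (0.6 to 0.8 SD for the range), a 50/50 factor, a two-sided 5% level, about 62 women and assumed band shares. It falls to about zero when the lowest or middle band is nearly empty.

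A reader might conclude that Aim 2 is underpowered or misses its target. Section 12b sets no target, so what is lost is sensitivity in an exploratory screen. Nor can the comparison with the worse cut be read as the plan's actual loss, because the plan chooses neither cut.

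**What to change.** Keep the yes/no count for stage 5 in the Aim 1 continuum. In Aim 2:

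1. Complete the urine band limits, so that 100 to 1000 ng/mL is assigned and low has a proper upper bound.
2. Test stage 5 factors against two ordered outcomes: the three-item self-report score (30-day recall) and the T2 urine TFV category. Use Mann-Whitney or Kruskal-Wallis for categorical factors, and Spearman or a proportional-odds model for continuous ones.
3. Report a yes/no version as secondary, with its cut stated in advance.
4. State that the urine result reflects recent dosing at T2 in women still taking PrEP, not adherence over T1 to T3.

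The cost is a short change to section 12a and one decision on band limits, with no new data, visits or participants. The downsides are one more exploratory outcome, which should be counted when the number of tests is reported, and results expressed as shifts in adherence level. The yes/no percentages remain available from Aim 1.
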